- The blinded investigator will assess the presence of residual NMB with the quantitative TOF monitor by calculating the average of 3 measurements of qTOF $T4/T1$ (40mA or adequate to achieve TOF response while comfortable for the patient) within 15min of PACU arrival and hourly until up to 3h after the end of surgery or sooner if the patient meets PACU discharge criteria. We will record the initial PACU TOF and calculate the PACU average TOF. After transfer to the postoperative floor, the blinded investigator will assess residual or recurrent NMB with the qTOF monitor twice a day, with 3 repetitions each time, and each assessment separated by ≥ 6 h. This will be maintained for up to 3 days after the end of surgery or until end of monitoring criteria are met.
- The individual doses of administered opioids received by the patient during the study (PACU and daily for up to 3 postoperative days or until the end of monitoring criteria are met) will be recorded and converted to morphine equivalents[21] to statistically evaluate the effect of opioid administration on hypoventilation events.
- Nursingcharted episodes of respiratory depression during the PACU stay will also be recorded. Postoperative pulmonary complications (as defined elsewhere[13]) during PACU and up to 3 postoperative days will be collected.

Postoperative end of study follow-up

At postoperative day 14 ± 3 during the patient's visit to the transplant surgery clinic or via a phone call, the PROMIS® Dyspnea Functional Limitations Short Form questionnaire will be repeated

and normalized to the patient's baseline. Any postoperative pulmonary complications[13] and hospital resources utilization occurring from the hospital discharge until this end of study follow-up will be collected from the patient and the medical record, and the estimated costs based on average hospital daily stay depending on type of care unit or reported cost of complications calculated.

Any signs and symptoms of hypersensitivity (e.g. rash, anaphylaxis) detected during PACU and up to 3 postoperative days will be collected from the patient and patient's providers. The relationship of these signs and symptoms to sugammadex will be assessed by the patient's providers and also by the study safety officer. Their confirmatory diagnostic testing and management will be performed at the discretion of the patient's providers.

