Frequency of patients with one or more episodes of hypoventilation events in PACU (primary outcome). This will be obtained from the noninvasive respiratory monitor that provides a continuous assessment of the patient's respiratory rate, tidal volume and minute volume. This continuous monitoring will be performed continuously during the PACU stay. When meeting PACU discharge criteria based on institutional standard of care (based on an Aldrete's score[33] ≥ 8 with patient's nurse and anesthesiologist agreement and no surgical concerns), the every 5-second information will be exported, and the periods with MV $<40\%$ of expMV for that patient that last ≥ 1 minute will

be identified and counted. For the primary outcome patients will be classified as presenting or not at least one event of hypoventilation, summarized per group and compared.

Frequency of patients with one or more episodes of hypoventilation events daily for 3 first postoperative days or sooner if patient meets end of monitoring criteria. Similar as before, hypoventilation will be assessed once daily for up to 3 days, or less if the patient is discharged from the hospital or is freely ambulating (ambulates outside of the hospital room ≥ 2 times a day) with no signs or symptoms of respiratory complications.

Additional assessments of hypoventilation (e.g. accumulated minutes of hypoventilation) will be performed during PACU and daily for up to 3 postoperative days.

Incidence of residual or recurrent NMB in PACU. This will be determined from the quantitative TOF measurements and calculated as the average qTOF T4/T1 at 40 mA from 3 repetitions at selected time points: 15min after arrival to PACU, hourly and before transfer to floor. A patient will be classified as presenting an episode of residual NMB if the average T4/T1 at any time point during PACU is <0.9 . In addition, a percentage of timepoints with an average T4/T1 <0.9 will be analyzed as an accumulated time with residual or recurrent NMB. This variable will be used as covariate in the logistic regression analysis (see below). An average TOF of 3 repetitions <0.4 will be considered a severe residual or recurrent NMB. Patient's safety will be prioritized and thus an average TOF of 3 repetitions <0.9 will be immediately reported to the patient's care team in addition to following the appropriate study regulatory safety communications of adverse events.

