Incidence of residual or recurrent NMB in the postoperative floor. This will be calculated as described before (T4/T1 <0.9 , considered severe if T4/T1 <0.4), as an average of 3 repetitions obtained on two occasions separated by ≥ 6 h daily on postoperative days 1-3 or until the end of monitoring criteria have been met.

Morphine equivalents will be calculated from individual opioid doses administered to each patient following standard conversion formulas[21, 40]. This morphine equivalent dose will be calculated for the PACU period and daily for 3 first postoperative days or until the end of monitoring criteria have been met, and used as covariate in the logistic regression analysis.

Time from NMBR administration to quantitative TOF T4/T1 >0.9 (minutes, one decimal). The quantitative TOF will be repeated at 80 mA every 30 seconds from the moment the NMBR medication (sugammadex or neostigmine) has been completely administered intravenously.

Time from NMBR administration to extubation (minutes, once decimal).

Time of total operating room time (minutes), counting from in-room time stamp to out-of-room time stamp.

The PROMIS® v1.0 Dyspnea Functional Limitations Short Form 10a_9-2-2016 questionnaire is a validated and standardized short questionnaire to quantitate if sugammadex used for NMBR reduces the subjective dyspnea scores relative to baseline. It will be completed by the patient in the preoperative phase and during the postoperative follow up. It is available at http://www.healthmeasures.net/administrator/components/com_instruments/uploads/PROMIS%20SF%20v1.0-Dyspnea%20Functional%20Limitations%2010a_9-2-2016.pdf.

Postoperative Pulmonary Complications (PPCs) following previous definitions[13, 41, 42], including:

Respiratory Failure, defined as[41]: "When postoperative $\text{PaO}_2 < 60\text{mmHg}$ on room air, a ratio of PaO_2 to inspired oxygen fraction < 300 or arterial oxyhemoglobin saturation measured with pulse oximetry (SpO_2) $< 90\%$ and requiring oxygen therapy".

Unplanned intubation with postoperative mechanical ventilation (POMV), defined as placement of a breathing tube that was not intended or planned, excluding instances of intubation during an unplanned return to the operating room. Also excluded those patients that were transferred intubated and ventilated to the intensive care unit (ICU) from the operating room.

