Kidney graft outcomes, including postoperative ClCr, daily urine output, need for dialysis postoperatively, diagnosis of delayed graft function, kidney graft rejection. Postoperative hemodialysis is not usually planned and typically reserved for patients with immediate donor graft failure who exhibit signs of congestive heart failure within the first week after transplantation. The need of rescue hemodialysis within the first week after kidney transplantation is an accepted and simple definition of delayed kidney graft function[46].

Hospital resources utilization: hospital floor length of stay (LOS) (days, rounded to half a day), ICU admission and LOS, estimated cost based on average daily cost at a postoperative UCH floor or ICU and/or based on reported estimated costs per PPC[47, 48]

Hypersensitivity adverse events: hypersensitivity signs and symptoms, including but not limited to rash, bronchospasm or anaphylaxis, will be obtained for up to 3 postoperative days directly from the patient and the patient's providers. Their relationship to sugammadex will be assessed by the patient's physicians and the study safety officer. Their confirmatory testing and management will be performed strictly at the discretion of the patient's physicians.

Statistical Methods

The primary hypothesis is that the frequency of patients with one or more episodes of hypoventilation events in PACU (% of patients) is lower in the sugammadex group compared to neostigmine (controls). This will be analyzed by logistic regression which includes as covariates group allocation, total morphine equivalents, and TOF T4/T1 response, and other observed significant and clinically relevant differences between the groups. The odds ratio for the group covariate will be the primary outcome of interest, with the other covariates included in the model to adjust for potential confounders related to hypoventilation.

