The secondary analysis comparing delayed efficacy of sugammadex to neostigmine in reducing the incidence of hypoventilation during the first 3 postoperative days will assume the same model and covariates as the primary hypothesis. To compare the incidence of PPCs a logistic regression model will be used with the binary outcome of any PPC and will include covariates for group and total morphine equivalents. Hospital length of stay and costs will be compared between groups using a linear regression model including covariates for group, total morphine equivalents, presence of respiratory comorbidities and other clinical differences that may influence the outcome. Continuous outcomes may be transformed if they violate the normality assumption (e.g., a log-transformation).

Multiplicity

Given only one primary outcome and hypothesis, there is a not a concern for multiplicity. Secondary analyses are considered exploratory in this protocol.

Power/Sample Size:

Based upon a sample size of 40 patients per group, this study has 90% power to detect a 50% difference in hypoventilation incidence in the PACU (from 76% as reported in previous studies[21] to 38%, alpha 0.05), assuming a potential dropout of up to 6 patients per group. The 50% reduction is considered clinically relevant for a decrease in the frequency of hypoventilation, a precursor of more clinically significant complications such as hypoxemia, reintubation or pneumonia. Quantifying the contribution of hypoventilation into more severe complications is challenging, and details of duration and severity of hypoventilation are not well known. Thus, only a significant reduction in hypoventilation incidence (i.e. 50%) may be accepted as relevant. This trial will provide additional detailed information that may provide more insight on the clinical consequences of hypoventilation (e.g. potential association between accumulated minutes of MV <40% expMV and decrease in SpO₂/FiO₂ over the following 30 min).

A sample size of 40 patients per group would also have approximately 80% power (78%) to detect a difference in case the incidence of any hypoventilation events is 60%, instead of the literature-based 76%. The table below provides the sample size per group to achieve a variety of assumptions for the primary outcome, alpha, and power:

Incidence Group 1	Incidence Group 2	Alpha	Power	Sample Size per Group
1. 0.76	2. 0.38	3. 0.01	4. 0.8	5. 39
6. 0.76	7. 0.38	8. 0.05	9. 0.8	10. 26

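### The primary model adjusts for PACU TOF ratio and opioid dose, both measured after reversal, so it does not estimate the 76% vs 38% effect for which 90% power is claimed

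*Combined protocol and SAP*

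**What the plan says.** Section III.F, Statistical Methods, defines the primary analysis: "This will be analyzed by logistic regression which includes as covariates group allocation, total morphine equivalents, and TOF T4/T1 response". Observed between-group differences judged relevant may be added. The odds ratio for group is the result of interest, "with the other covariates included in the model to adjust for potential confounders related to hypoventilation". The analysis of hypoventilation over three postoperative days "will assume the same model and covariates as the primary hypothesis".

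The timing is clear. Section III.C (Intraoperative phase) has the randomised drug given at the end of surgery. Section III.F takes TOF 15 minutes after PACU arrival, then hourly and before transfer to the floor, and says of the resulting variable: "This variable will be used as covariate in the logistic regression analysis (see below". On opioids it says: "This morphine equivalent dose will be calculated for the PACU period and daily for 3 first postoperative days".

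The form of the TOF covariate is not fixed. Section III.F offers a yes/no classification (any average below 0.9) and also says "a percentage of timepoints with an average T4/T1 <0.9 will be analyzed as an accumulated time with residual or recurrent NMB". Section III.C adds "We will record the initial PACU TOF and calculate the PACU average TOF". Statistical Methods speaks only of a TOF response.

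Under Power/Sample Size, with 40 per group and up to 6 dropouts in each, "this study has 90% power to detect a 50% difference in hypoventilation incidence in the PACU", meaning 76% falling to 38%. No covariate enters that calculation.

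**The concern.** The objective, the model and the power basis do not fit together. The primary objective concerns hypoventilation that results from incomplete reversal, so residual block is the pathway from drug to outcome. PACU TOF measures that block after the drug has acted. In a randomised comparison it is a consequence of treatment, not a confounder. A model that conditions on it asks whether sugammadex helps among patients with equal TOF recovery, and leaves out whatever the drug achieves by improving recovery.

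If part of the benefit runs through TOF, the primary odds ratio moves toward 1 and a real overall benefit may miss significance. Even with no mediation, TOF is correlated with group, which widens the standard error. This is the trial's only confirmatory test, and the 90% does not describe it. The open choice of TOF coding adds a decision that can change the result.

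For opioids the documents establish less. The dose accrues after reversal and in the same window as the outcome. Nothing says that the reversal agent changes it, so the direction of any bias is unknown.

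**Working it through.** **1. Reproduce the stated power.** Inputs from Power/Sample Size: p0 = 0.76, p1 = 0.38, alpha 0.05 (taken as two-sided), 40 − 6 = 34 evaluable per group. The pooled-variance formula without continuity correction is

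n = [z(0.975)·√(2·p̄·(1 − p̄)) + z(0.90)·√(p0(1 − p0) + p1(1 − p1))]² / (p0 − p1)², with p̄ = 0.57.

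n = [1.960 × √0.4902 + 1.282 × √0.4180]² / 0.1444 = 33.5, so 34 per group, as stated.

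The same formula gives the other three table rows (39, 26, 48) and 78.0% for 60% vs 30% at 40 per group (stated 78%). Power for 76% vs 38% is 90.4% at 34 per group and 94.5% at 40. One-sided testing would give 28 instead of 34, and a continuity correction 39. The plan's figures are therefore for an unadjusted comparison of two proportions. The matching marginal odds ratio is (0.38/0.62)/(0.76/0.24) = 0.194.

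**2. Is TOF affected by treatment?** By the plan's own figures, yes. Power/Sample Size takes residual block (T4/T1 below 0.9) as 36% after neostigmine (9 of 25 patients) and 5% after sugammadex.

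**3. Yes/no TOF covariate.** Assume the risk of hypoventilation given block, r, is the same in both arms, and keep the marginal risks at 76% and 38%. The risks without block are then (0.76 − 0.36r)/0.64 and (0.38 − 0.05r)/0.95. At r = 1 they are 62.5% and 34.7%. The most this route can explain is 0.31 × (1 − 0.625) = 11.6 of the 38 points at the neostigmine arm's no-block risk, or 0.31 × (1 − 0.347) = 20.2 points at the sugammadex arm's.

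**4. Continuous TOF covariate.** Assume normal TOF in each arm, with means z(0.36) − z(0.05) = 1.29 SD apart. The variance inflation of the group term is 1 + 1.29²/4, about 1.41. The intercept and slope are set to keep 76% and 38% at each assumed mediated share of the log-odds shift.

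**5. Simulated power of the group term** (logistic regression, Wald test, 34 per group, 4,000 replicates, block 36% vs 5%):

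| TOF coding | Assumption | Power |
|---|---|---|
| none (unadjusted) | all settings | 88–90% |
| yes/no | block does not affect risk | 84% |
| yes/no | r = 80% | 76% |
| yes/no | r = 90% | 63% |
| yes/no | r = 98% | 54% |
| continuous | nothing mediated | 77% |
| continuous | one quarter mediated | 55% |
| continuous | one half mediated | 32% |
| continuous | all mediated | 4% |

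The median adjusted odds ratio runs from 0.18 to 0.30 with yes/no coding. With continuous coding it is 0.19, 0.27, 0.39 and 1.03. At 40 per group, yes/no power is 90% down to 62%, and continuous power is 84%, 60%, 36% and 4%. A separate simulation with likelihood-ratio tests led to the same conclusion.

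**6. Other block rates, 34 per group.**
- 20% vs 5% (the 20% is assumed): yes/no 88% to 79%; continuous 84% (none mediated), 65% (a quarter), 43% (half).
- 10% vs 5% (low end of the 10–50% range that the plan cites): yes/no 89%; continuous 88% (none), 83% (a quarter).
- 50% vs 5% (high end): yes/no 78% to 25%; continuous 70% (none), 25% (half).

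No opioid term was simulated.

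**The case against.** The strongest reply is that the adjustment is deliberate. The hypotheses, the objectives and the restated hypothesis in III.C all call for adjustment for TOF and opioids, and III.G wants effects both through and apart from residual block. The sponsor could keep this estimand, state it openly and re-derive power for it. That would be coherent, and it means that the fix proposed here changes the stated estimand. But intent does not make the 90% apply to the adjusted test, and one adjusted odds ratio cannot give both effects. The adjusted effect is also open to confounding between TOF and hypoventilation, which randomisation does not remove and which could bias it either way.

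The size of the loss is fairly disputed:
- III.C speaks of 100 patients, or 50 per group. With yes/no coding and block 36% vs 5%, power at 44 evaluable per group (50 − 6) runs 93%, 88%, 76% and 65% from no effect of block to r = 98%. At 50 it runs from 95% down to 70–73%. Larger numbers soften the loss but do not remove it.
- The sentence naming the covariate follows threshold-based definitions, so the yes/no results fit the text better than the continuous ones. The percentage-of-timepoints coding was not simulated.
- Extubation requires T4/T1 above 0.9, which may narrow the gap between arms. The 36% comes from 25 general-anaesthesia patients, and the plan does not say whether that rule applied to them.
- The opioid case is weaker. If the agent does not alter opioid dose, adjusting for it is ordinary prognostic adjustment, and the odds ratio shifts only through non-collapsibility.
- The three-day analysis is exploratory by the plan's own statement.

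These points bear on magnitude and emphasis. They do not close the gap between the effect that was powered and the effect that is tested.

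**Conclusion.** The concern holds. The primary test conditions on a variable that the randomised drug is meant to change, while the sample size was derived for the total effect. That mismatch follows from the text and needs no assumption. The amount of power lost does rest on assumptions: the block rates, the risk given block or the mediated share, the TOF coding and the number evaluable. It ranges from almost nothing (10% vs 5%, yes/no coding) to severe (36% vs 5%, continuous coding, half mediated: 32% against 88–90% unadjusted). Under the plan's own block rates, threshold coding and 34 per group, the range is 54% to 84%. For opioids only the timing is established.

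**What to change.** Make the group comparison for the primary outcome, and for the three-day outcome, unadjusted or adjusted only for pre-specified covariates known before reversal. It then matches the existing calculation, with 90.4% power at 34 per group and 94.5% at 40 for the unadjusted contrast. Keep the TOF- and opioid-adjusted models as labelled exploratory analyses with one fixed TOF coding; these still serve the aim in III.G. Bring the adjustment wording in Clinical Hypotheses, Objectives and the III.C hypothesis statement into line. At lower priority, consider dropping postoperative morphine from the exploratory models for pulmonary complications, length of stay and cost.

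The cost is a protocol amendment, because the stated primary estimand changes from a TOF- and opioid-adjusted effect to the total effect. No extra patients, visits or data are needed, and the adjusted results are still reported.

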COMIRB Protocol

COLORADO MULTIPLE INSTITUTIONAL REVIEW BOARD
[name] [contact] [contact]

Protocol #: 18-2707

Project Title: A double-blind, randomized, parallel study to compare the efficacy of sugammadex versus neostigmine for reversal of neuromuscular blockade at the end of kidney transplantation surgery in patients with severe kidney dysfunction.

Principal Investigator: [name] M.D., Ph.D.

Version # and Date: #3 – 09/18/2020

Hypotheses and Specific Aims

Clinical Hypotheses

Sugammadex, compared to neostigmine, reduces inadequate neuromuscular blockade reversal (NMBR) and its related hypoventilation, as measured by reducing the frequency of patients with one or more episodes of hypoventilation, by at least 50% during the first 3h after the end of kidney transplantation surgery (or until meeting discharge criteria from the PACU if sooner than 3h) after adjusting for quantitative train-of-four (qTOF) T4/T1 monitoring and morphine equivalents received. Hypoventilation events are defined by the presence of ≥ 1 minute-long events of minute ventilation (MV) $<40\%$ of the expected MV for each patient (expMV).

Sugammadex, compared to neostigmine, reduces inadequate NMBR and its related hypoventilation, as measured by reducing the frequency of patients with one or more episodes of hypoventilation, by at least 50% for up to 3 days after kidney transplantation surgery after adjusting for qTOF T4/T1 monitoring and morphine equivalents received.

Our overall hypothesis is that sugammadex will provide improved NMBR and postoperative ventilation than neostigmine. Prevention of hypoventilation with sugammadex may contribute to reduce patient's reported dyspnea scores (PROMIS® Dyspnea Functional Limitation questionnaire scores), decrease PPCs possibly related to inadequate NMBR after kidney transplantation surgery (i.e. respiratory insufficiency, gastric aspiration, pneumonia), improve kidney graft outcomes, reduce hospital resources utilization and estimated healthcare costs. A study powered to test these as a hypothesis would require a substantially larger sample size and it may be pursued in the future.

Objectives

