Primary objective: To test the efficacy of NMBR with sugammadex, compared to neostigmine, to reduce inadequate NMBR and its related hypoventilation during the immediate postoperative period after kidney transplantation surgery, after adjusting for qTOF recovery and morphine equivalents received. We define hypoventilation as the incidence of ≥ 1 minute-long events of MV $<40\%$ of expMV. Minute ventilation will be measured continuously with a noninvasive respiratory volume monitor for the first 3h after the end of surgery or until meeting discharge criteria from the post-anesthesia care unit (PACU) (if sooner than 3h).

Secondary objective: To test the efficacy of NMBR with sugammadex, compared to neostigmine, to reduce inadequate NMBR and its related hypoventilation during the first 3 postoperative days in patients after kidney transplantation surgery, after adjusting for qTOF recovery and morphine equivalents received. We define hypoventilation as the incidence of ≥ 1 minute-long events of MV $<40\%$ of expMV. Minute ventilation will be measured continuously with a noninvasive respiratory volume monitor for up to 3d after surgery or until meeting end of monitoring criteria (if sooner than 3d)

Additional secondary objectives: To test if NMBR with sugammadex, compared to neostigmine, reduces patient's reported dyspnea scores (with the validated Patient-Reported Outcomes Measurement Information System, PROMIS®, assessment), decreases postoperative pulmonary complications (PPCs)

possibly related to inadequate NMBR after kidney transplantation surgery (i.e. respiratory insufficiency, gastric aspiration, pneumonia), improves kidney graft outcomes and reduces hospital resources utilization (i.e. hospital length of stay, ICU admission) and estimated healthcare costs.

II. Background and Significance/Preliminary Studies:

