We **hypothesize** that the intervention group will present a $\geq 50\%$ reduction in the incidence of hypoventilation for the first 3h after the end of kidney transplantation surgery or until meeting discharge criteria from the PACU (if sooner than 3h), as defined by the incidence of ≥ 1 minute-long events of observed MV of $<40\%$ of expMV detected with a noninvasive respiratory volume monitor after adjusting for qTOF T4/T1 and morphine equivalents received.

Tele-communication for screening, e-consenting and any eligible study-related visits

In line with current efforts to minimize face-to-face contact with potential candidates and/or study participants in response to the COVID-19 pandemic, we will maximize when possible HIPPA-compliant methods of tele-communication for any study-related tasks. HIPPA-compliant applications (i.e. REDCap, Qualtrics, MS Office, Zoom, Skype, or Vidyo) will be used for prospective study participants for electronic screening, consenting and any eligible study-related visits. The first goal of tele-communication with eligible candidates is to provide a detailed overview of the study protocol and consent form to be signed by study participant and PI (or research study staff).

- a. After subject screening, a phone call will be made to introduce the purpose of the study and to request prospective study participation, upon verbal consent, a personal e-mail address will be requested.
- b. After phone call, consent study forms in .pdf format will be sent via e-mail to prospective study participant with a follow up 30-minute video meeting request.
- c. During 30-minute video meeting, detailed e-consent guidance will be provided to prospective study participant.
- d. Participant will document and sign informed consent electronically or by printing the consent form, signing with pen, and then scanning and emailing back to study team.

After signed informed consent, all study-related visits will be evaluated for possible use of tele-communication. The study intervention during surgery and those postoperative in-hospital visits to assess respiratory function and residual NMB are not eligible for tele-communication, but all other visits for data collection from the participant (e.g. PROMIS questionnaires, end-of-study follow-up) will be attempted via tele-communication as described above.

D. Description, Risks and Justification of Procedures and Data Collection Tools:

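### The hypotheses claim a reduction of at least 50%, but the planned test is for superiority and the only named effect measure, an adjusted odds ratio, does not show the relative reduction

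*Combined protocol and SAP*

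**What the plan says.** All references are to the combined protocol and SAP.

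- **Clinical Hypotheses.** The first predicts fewer patients with hypoventilation "by at least 50% during the first 3h after the end of kidney transplantation surgery". The second predicts the same "by at least 50% for up to 3 days after kidney transplantation surgery". Both are stated after adjustment for qTOF and morphine equivalents.
- **III.C Study Design and Research Methods.** The hypothesis is repeated as a 50% or greater "reduction in the incidence of hypoventilation for the first 3h after the end of kidney transplantation surgery".
- **Objectives.** The primary objective carries no percentage. It is "to reduce inadequate NMBR and its related hypoventilation during the immediate postoperative period".
- **III.F Statistical Methods.** The primary hypothesis is that the percentage of patients "is lower in the sugammadex group compared to neostigmine (controls" group. The analysis is a logistic regression on group, total morphine equivalents, TOF T4/T1 and other observed between-group differences. "The odds ratio for the group covariate will be the primary outcome of interest".
- **III.F Variables/Time Points of Interest.** Each patient is classified as having or not having an event, and the result is "summarized per group and compared". Of the PACU TOF it says "This variable will be used as covariate in the logistic regression analysis", and PACU morphine equivalents are used in the same way.
- **III.F Power/Sample Size.** The design assumes a fall from 76% to 38%, with 60% as an alternative control incidence, and says that only a reduction of 50% may be accepted as relevant. The 3-day analysis uses the primary model and covariates.

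**The concern.** The plan sets two questions: whether the proportion is lower with sugammadex, and whether it is lower by at least half. Only the first is tested. Nothing says whether 50% is to be compared with a point estimate or a confidence limit, or is only a planning value. A significant result with a reduction of about 30% would satisfy the Objectives and Statistical Methods but fall short of the Clinical Hypotheses, III.C and the relevance sentence, and the plan does not say how it would be reported.

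The named measure does not help. The 50% is a relative reduction in a proportion. An odds ratio moves much further from 1 than the risk ratio when the outcome is as common as 60% to 76%. Anyone who reads it as a relative reduction would overstate the benefit.

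**Working it through.** **Inputs.** Power/Sample Size gives 76% and 38%, alpha 0.05, 90% power, 40 per group with up to 6 dropouts per group (34 left), and the alternative control incidence of 60%. III.C gives 100 patients in total, so 50 per group if allocation is 1:1 (an assumption).

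**1. Reproducing the plan's figure.** The two-sided pooled test of equal proportions, without continuity correction, has mean proportion (0.76 + 0.38)/2 = 0.57.

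n = [1.960 × √(2 × 0.57 × 0.43) + 1.282 × √(0.76 × 0.24 + 0.38 × 0.62)]² / 0.38² = [1.960 × 0.700 + 1.282 × 0.647]² / 0.1444 = 33.5, so 34 per group.

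This matches the plan. The other three table entries (39, 26, 48) and the 78% power for 60% against 30% at 40 per group also reproduce. The null hypothesis is therefore equality, with no 50% margin.

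**2. What a halving looks like as an odds ratio.**
- From 76%: (0.38/0.62) / (0.76/0.24) = 0.19.
- From 60%: (0.30/0.70) / (0.60/0.40) = 0.29.
- Conversely, OR 0.50 from 76%: odds 0.5 × 0.76/0.24 = 1.583, so the risk is 1.583/2.583 = 61.3%. The risk ratio is 0.613/0.76 = 0.81, a 19% reduction.

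**3. Results that just reach significance.** Control incidence about 76%, chi-square without correction, risk-ratio intervals by the log method:

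| Sugammadex vs neostigmine | p | Crude OR | Risk ratio (95% CI) |
|---|---|---|---|
| 18/34 vs 26/34 | 0.042 | 0.35 | 0.69 (0.48 to 1.00) |
| 21/40 vs 30/40 | 0.036 | 0.37 | 0.70 (0.50 to 0.99) |
| 28/50 vs 38/50 | 0.035 | 0.40 | 0.74 (0.55 to 0.99) |

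First row: OR = (18 × 8)/(16 × 26) = 0.35; risk ratio = 18/26 = 0.69; SE of its log = √(1/18 + 1/26 − 2/34) = 0.188; limits 0.69 × exp(±1.96 × 0.188). The reduction is 31%. In the first two rows the lower limits are 0.479 and 0.496, so a halving is not excluded. It is excluded only in the third row, which rests on the 1:1 assumption.

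**4. How often the two questions diverge.** Exact binomial enumeration with 76% against 38% true, as a share of all trials:

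| Per group | Significant | Significant, observed reduction <50% | Significant, observed reduction <40% | Upper 95% limit of risk ratio ≤0.50 |
|---|---|---|---|---|
| 34 | 90% | 37% | 10.5% | 1.2% |
| 40 | 95% | 41% | 13.0% | 1.3% |
| 50 | 98% | 45% | 13.8% | 1.3% |

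**5. Search for a measure on the right scale.** The per-group summary will yield two crude percentages. No risk ratio, risk difference or confidence interval is named anywhere.

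**The case against.** Powering a superiority test on a clinically relevant effect is normal practice. The Clinical Hypotheses and III.C can be read as the expected effect, and the relevance sentence as a justification of the planning value. The operative hypothesis in Statistical Methods says only lower, and a crude reduction is one division away from the per-group percentages. All of that stands, and it limits the point to wording and reporting. It does not supply an interval, a pre-specified measure or a rule for reading 50%.

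Three stronger readings are tempting, and the documents do not support them.

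- A reader might infer that the test or sample size is wrong. Step 1 shows that both are correct for superiority.
- A reader might take the 37% to 45% as damage done by the odds ratio. It is mostly sampling scatter: when the true reduction is exactly 50%, about half of all estimates fall short of 50% on any measure, and most of these significant results lie close to it, as the below-40% column shows.
- A reader might carry the crude odds ratios over to the planned analysis. The planned odds ratio is adjusted and the documents give no covariate effects, so its value cannot be computed.

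It is also fair to object that the hypotheses speak of a reduction after adjustment, so a crude risk ratio answers a different question. The revised text must therefore say which quantity the 50% is read against.

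**Conclusion.** The point holds as a mismatch between the claim, the test and the effect measure. It should be corrected, but it does not threaten the validity of the trial. Significance can arrive with a crude reduction of about 31% (34 per group) or 30% (40 per group), and the odds ratio that corresponds to halving depends on the control incidence.

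Nor can the trial be expected to establish a reduction of at least 50%. If the true reduction is exactly 50%, the chance that the upper 95% limit of the risk ratio reaches 0.50 or less is about 1%. The sensible reading of 50% is a planning effect and a benchmark for interpretation.

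The figures rest on unadjusted proportions, a two-sided alpha of 0.05 (sidedness is not stated, but two-sided reproduces the table) and the plan's own incidences.

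**What to change.** 1. **Wording.** Restate both Clinical Hypotheses and the one in III.C as superiority, with 50% as the planning effect, to match the Objectives and Statistical Methods. In Power/Sample Size, state that 50% is a benchmark for interpretation, that significance alone does not support a claim of at least 50%, and that the trial is not sized to establish such a claim, giving the chance of about 1%.
2. **Reporting.** In Statistical Methods, for both the PACU and the 3-day analysis, add the risk ratio and risk difference with 95% CIs. Take them from the per-group proportions or from a model with baseline covariates named before unblinding. Label them as the overall treatment effect, distinct from the odds ratio adjusted for TOF and opioid dose measured after randomisation. State that the 50% benchmark is read against this overall risk ratio.

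At the planned result the added line would read, for 13/34 against 26/34: risk ratio 0.50 (0.31 to 0.80), risk difference −38 points (Newcombe −56 to −15).

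**Cost.** Edits to a few sentences and a few lines of code. There are no new data, and the test, sample size and planned odds ratio are unchanged. The report must explain two effect measures, and the trial gives up any claim of at least 50% that rests on significance alone.
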